12.3.2 Missing data

Further details on dealing with missing data, along with the handling of possible outliers, will be described in the SAP. Other critical missing data, if any, will be discussed during the review of the data. Decisions will be fully documented in the Data Review Report.

Clinical Study Code No.: CLI-10067AA1-01	Version No.: 6.0
EUDRACT No.: 2022-001079-15	Date: 06 July 2023

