1.2 STUDY DESIGN

[figure not shown]
This is a Phase Ib, multi-centre, multi-country, randomised, double-blind, placebo-controlled study to investigate the safety, tolerability, immunogenicity, and PK of single IV doses of CHF10067 in subjects with IPF. The effect of CHF10067 on TG2 levels will also be investigated as an exploratory endpoint.

Overall, 24 subjects will be enrolled in 3 cohorts (Cohorts A [1000 mg], B [anticipated 2000 mg], and C [anticipated 3000 mg]) consisting of 8 subjects per cohort. In each cohort, 6 subjects will receive CHF10067, and 2 subjects will receive placebo.

The doses will be administered according to an escalation scheme designed to ensure sufficient safety conditions for subjects. In each cohort, subjects will be divided into 2 sub-groups, with each sub-group being dosed at least 24 hours apart. The first sub-group will comprise 2 subjects, with 1 subject receiving CHF10067 and 1 subject receiving placebo. The second sub-group will comprise 6 subjects, with 5 subjects receiving CHF10067 and 1 subject receiving placebo. Continuation to dose the remaining 6 subjects will be evaluated by at least the Medical Monitor and Sponsor Clinical Research Physician based on the safety data provided by the Investigator(s) where the first-sub-group have been dosed. The decision to escalate to the next dose will be made by the Safety Advisory Committee when safety data until Day 14 have been collected for all subjects at the previous dose level. Pharmacokinetic and

immunogenicity data will also be included in the safety evaluation for dose escalation (if available) but are not mandatory to escalate to the next dose.

An overview of the study design is shown in the figure below.

The schedule of assessments is in appendix 10.1.

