2.2 IMMUNOGENICITY

2.2.1 *Available data*

Serum samples for anti-drug antibody (ADA) assessments will be conducted utilizing a tiered approach (i.e., screen, confirm, titer), and ADA data will be collected pre-dose and at Days 14, 28, 56, and 84 and in case of early termination visit.

[figure not shown]
ADA result from each sample will be reported as either:

- ADA-positive: when ADA is detected at both screening and confirmatory tests in a sample, the sample is considered positive.
- ADA-negative: when ADA is not detected at screening test OR ADA is detected at screening but not detected at confirmatory test, the sample is considered negative.
- ADA-unevaluable: when a sample could not be tested for ADA status (“un-assayed sample”) due to inadequate sample volume, mishandling, or errors in sample collection, processing, storage, etc., either at screening or confirmatory test.

If the confirmatory sample is positive (i.e., ADA-positive sample), the ADA titer will be reported as well. ADA titer is a quasi-quantitative expression of the level of ADA in the sample.

In addition, the presence of neutralizing antibody (nAb) will be tested for all ADA -positive samples using a ligand-binding assay. The nAb results will be reported as either positive or negative.

ADA sample results

2.2.2 *Derivation rules*

No data imputation will be performed for missing and/or unevaluable samples.

Using the sample ADA status, subjects will be classified using the following definitions:

- **ADA evaluable subject**: A subject with baseline sample and at least one sample taken after drug administration during the treatment periods that are appropriate for ADA testing (i.e., with reportable result).
- **ADA unevaluable subject**: A subject without an evaluable sample at baseline OR with reportable baseline result but without a single sample taken (or without a reportable result) after drug administration during the treatment period.
- **ADA-positive subject (ADA+)**: A subject with at least one treatment-induced or treatment-boosted ADA-positive sample at any time during the treatment period. See definitions of treatment-induced and treatment-boosted ADA in Section 2.2.3.
- **ADA-negative subject (ADA-)**: A subject without a treatment-induced or treatment-boosted ADA-positive sample during the treatment period.

2.2.3 *Presentation of results*

The number and percentage of subjects who fulfil the below criteria will be presented by treatment.

- **Baseline ADA-positive**

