For this group of subjects, titer range (median and interquartile range (IQR)) of the baseline ADA-positive samples will be reported.
- **ADA positive at any visit (ADA prevalence)**
A subject with at least one positive ADA result available at any time, including baseline (i.e., pre-existing ADA) and post-baseline measurements (i.e., ADA+). For this group of subjects, peak positive titer and range (median, IQR) will be reported.
- **ADA incidence**
 - **Treatment-induced ADA**, defined as ADA developed de novo (seroconversion) following drug administration (i.e., formation of positive ADA any time after the drug administration in subjects with ADA-negative baseline).
For this group of subjects, the following additional parameters will be presented:
 - Peak positive titer and range (median, IQR);
 - **Onset of ADA**
Time to onset of ADA (i.e., time period between the initial administration of the drug and the first instance of treatment-induced ADA);
 - **Duration of ADA**
 - **Persistently positive ADA**
Subjects having a treatment-induced ADA detected at

least two non-consecutive time points, with the last ADA-positive measurement (irrespective of any negative samples in between first and last positive measurements) being detected at the end of the study period (i.e., day 84) for completer subjects or at the last available sampling time point for prematurely discontinued subjects.

- *Transiently positive ADA*

Subjects having a treatment-induced ADA not fulfilling the above condition for persistently positive.

- Treatment-boosted ADA, defined as a baseline positive ADA titer (i.e., pre-existing ADA) that was boosted to a 4-fold or higher level following drug administration.

For this group of subjects, the fold increase in titer (ratio of peak post-administration titer to baseline titer) and range of titer increases (median, IQR) will be presented.

The combination of both treatment-induced and treatment-boosted ADA (i.e., the percentage of patients fulfilling this criterion) is defined as ADA incidence.

- nAb positive at any visit (including baseline and all post-baseline measurements).

All immunogenicity data will be listed.

Only if immunogenicity data will allow (i.e., if the number of ADA+ subjects will be ≥ 3), the effect of immunogenicity on PK and safety will be evaluated:

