5. GENERAL CHARACTERISTICS ANALYSES

5.1 SUBJECT DISPOSITION

The following subject data will be tabulated by treatment and overall:

- The number of screen failures
- The number and percentage of subjects who completed or discontinued the study as documented on the study termination page and the number and percentage of subjects for each study discontinuation reason
- The number of subjects in each analysis set
- The number and percentage of subjects for each analysis visit

All information collected in the eCRF concerning allocation, code breaking, study discontinuation and information on phases, dates of first signed informed consent, last visit and last contact (over the whole study) will be listed.

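### SAP 2.2.3 calls treatment-induced ADA transient without requiring a later negative sample, so some subjects still positive at their last evaluable sample are counted as transient

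*SAP*

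**What the plan says.** Under Duration of ADA, SAP 2.2.3 divides subjects with treatment-induced ADA into two classes.

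- **Persistent:** ADA detected at, in the SAP's words, "least two non-consecutive time points, with the last ADA-positive measurement" "being detected at the end of the study period (i.e., day 84) for completer subjects or at the last available sampling time point" for subjects who discontinued early. A parenthesis in the same sentence says that negative samples between the first and last positive do not matter.
- **Transient:** "Subjects having a treatment-induced ADA not fulfilling the above condition for persistently positive".

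On sampling, SAP 2.2.1 states: "ADA data will be collected pre-dose and at Days 14, 28, 56, and 84 and in case of early termination visit". It also defines an unevaluable sample. On gaps, SAP 2.2.2 states: "No data imputation will be performed for missing and/or unevaluable samples".

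SAP 2.2.3 does not define completer. The only source of completion status is SAP 5.1, which tabulates "The number and percentage of subjects who completed or discontinued the study as documented on the study termination page". Protocol 12.3.2 says of missing data in general: "Other critical missing data, if any, will be discussed during the review of the data". It gives no rule for ADA. The changes listed in SAP 7.1 leave the definitions as they are.

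The classification is tabulated in Table 14.2.4.1, marked as a key first result.

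**The concern.** A reader takes *transient*, under a heading on duration, to mean that the antibody appeared and then went away. The rule does not require that. It assigns the label to anyone who misses the persistent definition, including subjects whose last result is positive.

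The two branches of the persistent definition are also unequal. A discontinued subject is judged at the last available sample, but a completer must be positive at Day 84. With no imputation, a completer without an evaluable Day 84 result cannot be persistent, whatever the other samples show. Such gaps are foreseeable: SAP 2.2.1 provides for unevaluable samples, and Protocol 9.2 allows assessments to be missed in a health emergency.

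Immunogenicity is a secondary objective, and Protocol 1.2 says these data will help set doses for later studies. In the cases described here the error runs one way: unresolved positivity is reported as transient.

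**Working it through.** The documents give no figure to reproduce. The check applies the rule to every possible result pattern in a baseline-negative subject.

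**Inputs.** Four post-dose samples, at Days 14, 28, 56 and 84 (SAP 2.2.1). The persistent and transient definitions (SAP 2.2.3). No imputation (SAP 2.2.2). Six active subjects in each of three cohorts (SAP 1.2), so 3 × 6 = 18.

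**Two readings of non-consecutive**, since the SAP does not define it:

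- Reading A, *not adjacent*: the first and last positives are at least two scheduled samples apart.
- Reading B, *need not be consecutive*: any two positives qualify.

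**Step 1. Completers with all four samples evaluable.** There are 2⁴ − 1 = 15 patterns with at least one positive, and 2³ = 8 of them are positive at Day 84.

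- Reading A: persistent needs Day 84 positive plus Day 14 or Day 28 positive. That removes Day 84 only and Days 56 + 84 only, so 8 − 2 = 6 are persistent and 15 − 6 = 9 transient. Two of the 9 are positive at the last sample.
- Reading B: only Day 84 alone is removed, so 8 − 1 = 7 are persistent and 15 − 7 = 8 transient. One of the 8 is positive at the last sample.

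Day 84 only is therefore transient on both readings, with no missing data involved.

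**Step 2. Same results at Days 14, 28 and 56, no evaluable Day 84 sample.** There are 2³ − 1 = 7 patterns, 4 of them positive at Day 56.

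| Status | Persistent / transient, reading A | Persistent / transient, reading B |
|---|---|---|
| Completer | 0 / 7 | 0 / 7 |
| Discontinued, Day 56 last available | 2 / 5 | 3 / 4 |

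Positive at all three days is transient for the completer and persistent for the discontinued subject, on either reading.

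**Step 3. Discontinued subjects with Day 28 as the last available sample.** There are 3 patterns: 0 persistent / 3 transient on reading A, 1 / 2 on reading B. Positive at both days is the pattern that changes label between readings.

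**Step 4. Require a negative last evaluable sample for transient, and use one anchor for everyone.**

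| Patterns | Transient / persistent / indeterminate, reading A | Transient / persistent / indeterminate, reading B |
|---|---|---|
| 15, all four samples evaluable | 7 / 6 / 2 | 7 / 7 / 1 |
| 7, last evaluable sample Day 56 | 3 / 2 / 2 | 3 / 3 / 1 |

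The second row now applies equally to completers and discontinued subjects.

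**Step 5. Effect of one subject.** 1/6 = 16.7 percentage points in a dose group, and 1/18 = 5.6 over all active subjects, if the denominator is all treated subjects. If it is treatment-induced subjects only, the shift is larger.

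**The case against.** **Completer is undefined.** If it meant only subjects with an evaluable Day 84 sample, the unequal treatment might seem to disappear. It does not. A subject who finished the study without that sample would then be neither a completer nor prematurely discontinued, would meet neither branch, and would still fall into the remainder. The Day-84-only case does not depend on this at all.

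**Existing procedures could fill a gap.** SAP 6.2.4 allows an unscheduled visit to be reallocated to the planned visit it replaces, and Protocol 12.3.2 sends critical missing data to documented review. The first helps only if a replacement sample exists; the second is a case-by-case decision.

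**A residual class is a legitimate prespecified choice.** One positive at the last sample is no evidence of persistence, and a two-class rule has to put it somewhere. That is fair, but it argues for a third class rather than for a label stating a duration that was not observed. SAP section 8 cites a harmonised terminology paper; whether the split follows it cannot be judged from these documents.

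**The SAP's wording on intervening negatives fits reading B.** It does, without settling the point. The request to define the term is a clarification, and the concern does not rest on it.

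**A common anchor has a cost.** On reading B, a completer positive at Days 14 and 28 with both later samples unevaluable would become persistent on samples 14 days apart. This is true, but the SAP on that reading already treats a discontinued subject with those results as persistent. Reading A would put both in the indeterminate row.

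**The consequences are small.** This stands. Escalation does not require immunogenicity data, the PK and safety displays use only ADA-positive or ADA-negative status, and time to onset is reported for the same group, so late seroconversion can be seen.

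**Conclusion.** The concern holds. Followed exactly, the SAP reports as transient a completer first positive at Day 84, and it gives opposite labels to identical results according to completion status when Day 84 is not evaluable. The Days 56 + 84 pattern, and two adjacent positives at the end of a discontinued subject's record, are affected only on reading A.

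The size is limited. Only the persistent and transient rows of Table 14.2.4.1 are affected, and both are descriptive; the SAP adds this split to the tables in Protocol 12.3.5.3. ADA incidence, prevalence, titres and ADA-positive/negative status are unchanged. Listing 16.2.6.1 shows the final ADA status, so affected subjects can be found by hand, although the tabulated count would remain wrong. The number affected may be zero or a few of 18. The figures above count patterns and are not probabilities, because the documents give no ADA rate or onset distribution. The correction should be made, but no trial decision set out in the documents depends on it.

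**What to change.** In SAP 2.2.3:

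1. Define transient as treatment-induced ADA with a negative last evaluable sample.
2. Judge persistence at the last evaluable sample for completers and discontinued subjects alike.
3. State whether non-consecutive means not adjacent or need not be consecutive.
4. Add a row to Table 14.2.4.1 for subjects positive at the last evaluable sample who do not meet the persistent definition, labelled as duration indeterminate.

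The cost is a change of SAP wording and one table row, using data already planned for collection.

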1.3 EXPECTED SAMPLE SIZE

This study is designed to explore the safety and tolerability of CHF10067 for the first time in subjects affected by IPF, while exposing a minimum number of subjects; therefore, no formal power calculation was performed.

A sample size of 24 subjects (8 subjects per cohort; 6 treated with CHF10067 and 2 with placebo) is deemed adequate to assess safety and tolerability of CHF10067. In each cohort, a minimum of 2 subjects are required to be not receiving antifibrotic treatment (including subjects with previous use of antifibrotic treatment that has been stopped for at least 2 weeks prior to screening).

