- **PK:** Serum concentration/time curves will be presented in linear/linear and log/linear scale. Plots will be presented by dose level and subject ADA status (i.e., ADA+ or ADA-), based on arithmetic means;
- **Safety:** The number and percentage of patients with treatment-emergent AEs will be summarized by subject ADA status (i.e., ADA+ or ADA-), in line with the summary reported in Section 3.1.3.

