3. SAFETY ANALYSES

3.1 ADVERSE EVENTS

3.1.1 *Available data*

Adverse events (AEs) are coded into system organ classes and preferred terms using the medical dictionary for regulatory activities (MedDRA, see section 10.3). For each AE, start and stop date(time)s are collected as well as intensity, a seriousness flag, seriousness criteria, treatment-relationship, action taken towards the study treatment and outcome.

Immediate hypersensitivity reactions (IHRs) are collected in a dedicated eCRF and are coded according to MedDRA dictionary (see section 10.3). For each IHR, start and stop date(time)s are collected as well as associated signs/symptoms, severity and suspected anaphylaxis.

3.1.2 *Derivation rules*

Pre-treatment AEs are defined as AEs starting between date of informed consent with 00:00 added as time part and the date(time) of first study treatment administration – 1 minute, extremes included.

Treatment-emergent adverse events (TEAE) are defined as AEs starting on or after first administration of any study treatment.

Adverse drug reactions (ADRs) are defined as TEAEs related to study treatment or with missing relationship.

Based on their start date(time), AEs will be allocated to the phase during which they started. Phases are defined in section 6.2.1. In case the AE start date(time) is incomplete or missing and the AE could consequently be allocated to more than one phase, a worst-case allocation will be done as detailed below:

- Treatment phase vs. non-treatment phase: AE will be allocated to the treatment phase.

A fatal AE is defined as an AE with outcome 'fatal'.

An AE for which the study treatment was discontinued is defined as an AE with action taken 'drug permanently withdrawn'.

	Statistical Analysis Plan	
CLI-10067AA1-01	Final Analysis	Final 1.0 of 30MAY2024

AE onset and duration will be calculated as follows:

- AE onset day (vs. first administration) =
 - AE start date < date of first administration: AE start date – date of first administration
 - AE start date \geq date of first administration: AE start date – date of first administration + 1 day
- AE duration (rounded as detailed in section 6.3.4) =
 - If start and stop date(time)s are available:
 - AE end date(time) – AE start date(time) + 1 minute

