6.2 PHASES AND TIME POINTS

6.2.1 Phases

Adverse events, medications, and procedures will be allocated to phases. All other analyses will not be allocated to phases. Instead, the visit and time point labels indicated on the subject's electronic case report form (eCRF) will be used to allocate the assessments. Early termination assessments will be allocated to the treatment phase.

Adverse events and medications:

Phase	Start	End
Screening	Date of signing the ICF, with 00:00 added as time part	First administration date(time) – 1 minute
Treatment	First administration date(time)	Date of last contact, with 23:59 added as time part

Per definition, and for each subject, the first phase starts on the date of the earliest available ICF signature, with 00:00 added as time part. The last available phase ends on the date of last contact, with 23:59 added as time part.

Procedures:

Phase	Start	End
Screening	Date of signing the ICF	First administration date – 1 day
Treatment	First administration date	Date of last contact

Per definition, and for each subject, the first phase starts on the date of the earliest available ICF signature. The last available phase ends on the date of last contact.

AEs, medications, and procedures will be allocated to phases as described in sections 3.1.2 and 5.5.2 respectively.

All PK records (PK concentrations and PK parameters) and IHRs will be allocated to the treatment phase.

	Statistical Analysis Plan	
CLI-10067AA1-01	Final Analysis	Final 1.0 of 30MAY2024

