14.2.2.2	CHF10067 Serum Concentrations (ng/mL) by Scheduled Time (PK Set) Individual values and descriptive statistics of CHF10067 serum concentrations per dose level	PK	PCT002
14.2.2.3	CHF10067 Serum PK Parameters (PK Set) Individual values and descriptive statistics of CHF10067 serum PK parameters, per dose level	PK	PKT001
14.2.2.4	Dose Proportionality Assessment of CHF10067 Serum PK Parameters (Power Model) (PK Set) The slope and 90% CI of the power model will be tabulated by PK parameter of CHF10067 (AUC _{0-t} , AUC _{inf} , and C _{max})	PK	
IMMUNOGENICITY			
14.2.4.1	Summary of ADA Responses (Safety Set) [KFR] Tabulation of the number and percentage of subjects as classified in section 2.2.3.	SAF	
14.2.4.2	Summary of TEAEs by Subject ADA Status (Safety Set) Tabulation of the number and percentage of subjects with at least one TEAE by subject ADA status (ADA+ or ADA-). Note: if the number of ADA+ subjects is less than 3, this table will be generated without results. Instead, an informative message will be printed in this output.	SAF	AET001
SAFETY			
ADVERSE EVENTS			
14.3.1.1	Summary of TEAEs (Safety Set) [KFR] Tabulation of the number and percentage of subjects with at least one of the events described in the SAP. The number of events will also be shown.	SAF	AET001
14.3.1.2	TEAEs by System Organ Class and Preferred Term (Safety Set) Tabulation of the number and percentage of subjects with TEAEs by MedDRA system organ class and preferred term. The number of events will also be shown.	SAF	AET003

	Statistical Analysis Plan		
CLI-10067AA1-01	Final Analysis	Final 1.0	of 30MAY2024

Number	Title	Analysis Set	TLFs Library Template Number
14.3.1.3	Serious TEAEs by System Organ Class and Preferred Term (Safety Set) Tabulation of the number and percentage of subjects with serious TEAEs by MedDRA system organ class and preferred term. The number of events will also be shown.	SAF	AET003
14.3.1.4	Non-Serious TEAEs by System Organ Class and Preferred Term (Safety Set) Tabulation of the number and percentage of subjects with non-serious TEAEs by MedDRA system organ class and preferred term. The number of events will also be shown.	SAF	AET003
14.3.1.5	ADRs by System Organ Class and Preferred Term (Safety Set) [KFR] Tabulation of the number and percentage of subjects with ADRs by MedDRA system organ class and preferred term. The number of events will also be shown.	SAF	AET003

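### The table of TEAEs by ADA status counts events from Day 1 under an ever-positive label, so for treatment-induced ADA it shows events that precede the first positive sample as ADA+ events

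*SAP*

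**What the plan says.** SAP 2.2.3 makes the display conditional on at least 3 ADA+ subjects and presents it as the assessment of what immunogenicity does to safety: "The number and percentage of patients with treatment-emergent AEs will be summarized by subject ADA status". The same sentence says it should match the overview in SAP 3.1.3. SAP 9.1 lists it as Table 14.2.4.2, on the Safety Set, with the same template as the main TEAE summary (Table 14.3.1.1).

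The two variables that it crosses are defined as follows.

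- **Events.** SAP 3.1.2: "Treatment-emergent adverse events (TEAE) are defined as AEs starting on or after first administration of any study treatment". The treatment phase in SAP 6.2.1 ends at "Date of last contact, with 23:59 added as time part". The SAP 3.1.3 overview also has a row for immediate hypersensitivity reactions.
- **Status.** SAP 2.2.1: "ADA data will be collected pre-dose and at Days 14, 28, 56, and 84 and in case of early termination visit". Under SAP 2.2.2 one treatment-induced or treatment-boosted sample, whenever it occurs after dosing, makes the subject ADA+. A subject with no such sample is ADA-.

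No rule links the onset of an event to the date of the first positive sample.

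**The concern.** The two variables start at different times. A TEAE can begin at the start of the infusion. A treatment-induced positive result cannot be seen before the first post-dose sample and may first appear at Day 84. The status is then applied back over the whole follow-up.

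Immediate hypersensitivity reactions show the consequence most plainly. Protocol 7.2.2.5.1 places them during the infusion or in the 24 hours after it. A reader looking for an antibody effect would probably turn to that row first. Yet a Day 1 reaction in a subject who was negative at baseline and first positive at Day 56 would stand under ADA+. At stake is how the one display meant to relate antibody to safety is read. The primary safety tables by treatment are not affected.

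**Working it through.** **Design figures.** SAP 1.2: "In each cohort, 6 subjects will receive CHF10067, and 2 subjects will receive placebo". Three cohorts give 3 × (6 + 2) = 24 subjects, as stated, of whom 18 are active and 6 placebo. On size, SAP 1.3 says "no formal power calculation was performed", so there is no power or ADA-rate figure to reproduce.

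**Time scale.** SAP 6.2.3 makes the dosing date Day 1, so Day d is d − 1 days after dosing and Day 84 is 83 days after. The PK windows in SAP 6.2.4 agree: the Day 14 target is 312 h = 13 × 24, and the Day 84 target is 1992 h = 83 × 24.

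**Share of follow-up before the first positive sample,** (d − 1)/83. True onset lies between the last negative and the first positive sample, so the share before the last negative sample is shown as a lower bound.

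| First positive | Before first positive | Before last negative | On or after first positive |
|---|---|---|---|
| Day 14 | 13/83 = 15.7% | 0% (pre-dose) | 84.3% |
| Day 28 | 27/83 = 32.5% | 13/83 = 15.7% | 67.5% |
| Day 56 | 55/83 = 66.3% | 27/83 = 32.5% | 33.7% |
| Day 84 | 83/83 = 100% | 55/83 = 66.3% | 0% |

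The ±2-day visit window (Protocol 7.1) moves the Day 14 figure from 11/83 = 13.3% to 15/83 = 18.1%. An early-termination sample could come sooner.

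**Share of subjects affected (illustration).** Assume a constant hazard and a proportion P with a TEAE by Day 84. Then h = −ln(1 − P)/83, and the share of those subjects whose first TEAE precedes Day 14 is [1 − exp(−13h)]/P. P is not given in the documents, so a range is used.

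- P = 0.3: 0.054/0.3 = 18%
- P = 0.5: 0.103/0.5 = 21%
- P = 0.7: 0.172/0.7 = 25%
- P = 0.9: 0.303/0.9 = 34%

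Clustering of events around the infusion would raise these shares.

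**Hypersensitivity reactions.** There is one dose, reactions arise within 24 hours of it, and the first scheduled post-dose sample is no earlier than Day 12. No scheduled sample can therefore show treatment-induced ADA at the time of a reaction.

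**Who counts as ADA-.** SAP 2.2.2 defines ADA- only by the absence of an induced or boosted sample. Read literally, a subject classed as ADA-unevaluable also meets it, and SAP 6.4.1 uses the whole analysis set as denominator for event data.

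**The case against.** The strongest reply is that this is a small descriptive table and that the plan does not rest on it. No test or attribution is planned. Time to ADA onset is summarised (SAP 2.2.3) and listed (Listing 16.2.6.1), AE onset day is in Listing 16.2.7.2, and hypersensitivity reactions have their own listing (16.2.7.10). With at most 18 active subjects, the order of events can be read subject by subject. Reactions also have their own pathway: CHF10067 IgE is measured before dosing and after a reaction (Protocol 7.2.2.5), positive ADA samples are tested for IgE (7.2.2.4), and the Safety Advisory Committee characterises reactions at the end of the study (7.2.2.5.1). All of this stands and keeps the point minor. It does not mend the table, because the reader must match separate listings by hand to answer the question it is meant to address.

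Three stronger readings are tempting, and the documents do not support them.

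- **That placebo subjects are pooled into ADA-.** The Safety Set includes them, and the table is described only by ADA status. Pooling would make placebo 6/(24 − 3) = 28.6% of ADA- with 3 active ADA+ subjects. With assumed TEAE rates of 50% active and 20% placebo and no ADA effect, it would create a difference of 0.50 − (15 × 0.50 + 6 × 0.20)/21 = 8.6 points. With equal rates the difference is 0. But the table is tied to SAP 3.1.3, which is by treatment. SAP 6.4.3 makes presentation by treatment the default, and SAP 7.1 says that the SAP's analyses separate active from placebo. Pooling is therefore not planned.
- **That the counted events precede any antibody.** Treatment-boosted subjects had ADA at baseline. In induced subjects, antibody may have been present before the first positive sample.
- **That the table is uninformative.** It remains a valid description of full-period TEAEs by eventual ADA status.

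**Conclusion.** The timing point holds for treatment-induced ADA. Events from Day 1, including immediate hypersensitivity reactions, appear under ADA+ without evidence that antibody was present. The period concerned runs from about 16% of follow-up (first positive at Day 14) to all of it (Day 84). These shares follow from the visit schedule alone. The 18% to 34% of subjects with a first TEAE before Day 14 rests on the assumed hazard and TEAE rates.

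The importance is low. The table is conditional and descriptive, and at its 3-subject minimum the exact 95% CI for 1 of 3 is 0.8% to 90.6%. Separation of placebo is already the plan's rule and needs only confirmation in this table. The literal inclusion of unevaluable subjects in ADA- is a small gap that the same edit can close.

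**What to change.** In SAP 2.2.3 and the entry for Table 14.2.4.2:

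1. Keep the full-period TEAE count by ADA status as the ADA+ versus ADA- comparison.
2. For treatment-induced ADA+ subjects, add a split of TEAEs by onset before versus on or after the first positive sample.
3. Show treatment-boosted subjects separately, since they had ADA at baseline.
4. State that the table covers ADA-evaluable subjects who received CHF10067. If all 18 active subjects are evaluable and k are ADA+, the comparator is 18 − k: 15, 12 or 9 for k = 3, 6 or 9.
5. Describe the table as descriptive.

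The cost is one derived flag, one added column and a few lines of text, because the SAP already derives AE onset day and time to ADA onset. There are two downsides to footnote. Onset of ADA is known only to the sampling interval, so some events labelled as earlier may have occurred with antibody present. Post-onset percentages also cover shorter and unequal windows (84% of follow-up down to none), and ADA- subjects have no matching time origin, so these percentages should not be compared directly with full-period ADA- percentages.
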